#### 8.2.7 WITHDRAWAL FROM STUDY

Participants will have the right to withdraw from the study at any time after consent. Data collected up to the point of withdrawal will be used unless the participants expressly did not wish researchers to use the data.

During recruitment of participants for interviews, the researcher will contact consented parents approximately 2 to 3 months after PICU transport to confirm that they still wish to participate and to answer any questions they might have about the study. Similarly, at 12 month follow up, parents will be contacted to confirm they still wish to participate in the study and to complete follow up questionnaires. If the parents wish to withdraw from the study, they can do so at any time without providing a reason; if a reason for withdrawal is provided, it will be recorded.

#### 8.3 Workstream C: Health economic evaluation

This work stream will address the following objective of the DEPICT study: Objective 2.1: To perform cost effectiveness analyses of PICRT provision for critically ill children, comparing different service models currently in use.

#### 8.3.1 APPROACH

We will evaluate the costs and value for money of different ways PICRTs are currently organised to identify the most cost-effective model. The data sources described in the quantitative analysis (workstream A) will be supplemented with cost data and the assembled dataset of individual observational patient-level data will be used to compare different PICRT models. The primary health outcome measure for the health economic evaluation will be the number of lives saved in each strategy, and the secondary outcome will be quality-adjusted life years. A detailed cost analysis of each identified PICRT model will be undertaken based on team composition, interventions performed and critical incidents. The statistical analysis will aim to identify differences in lives saved, QALYs gained and cost differences between different ways in which PICRTs are organised. We will evaluate costs and mortality at 30 days following PICU admission (the primary outcome in the quantitative analysis; short-run analysis), costs, mortality and QALYs at one year following PICU admission (the final follow-up point in the study; medium-run analysis), and lifetime costs and QALYs (long-run analysis). A UK NHS and personal social services (PSS) perspective will be adopted for the short- and medium-run analyses, though PSS cost are expected to be small; in the long-run analysis, an NHS/PSS perspective will be adopted in the base case and a societal perspective will be adopted in sensitivity analysis.

#### 8.3.2 MEASURING COSTS

There are three elements of the cost analysis: costs of PICRT transport; NHS/PSS costs in the shortand medium-run; and, NHS/PSS and societal costs in the long-run. A detailed cost analysis of transport by the PICRT will be carried out based on travel time, team composition, interventions performed and management of critical incidents. Unit costs for each of these items will be obtained from provider Trusts and 2014-2015 NHS Reference costs.

For NHS/PSS costs in the short- and medium-run, the main health care resource use categories following arrival at the PICU will include time spent in the PICU (also accounting for time on invasive ventilation, vasoactive agent therapy, renal replacement therapy and extra-corporeal life support), time spent on different wards in the hospital after discharge from the PICU, and the number of inpatient and day case admissions, A&E visits and outpatient visits up to one year. Unit costs for these items will be taken from 2014-2015 NHS Reference Costs. It will not be possible to measure costs outside the hospital during the first year (e.g., primary care costs) directly for each patient included in the analysis, but we will estimate these based on published estimates of primary care resource use associated with main diagnosis leading to PICU admission. These will be obtained from systematic literature searches. While there is considerable uncertainty in these costs, we expect them to be a small proportion of total costs when combined with hospital costs. Hence the uncertainty is unlikely to affect the results, though we will examine this in sensitivity analyses.

Long-run costs will be modelled from published sources based on systematic literature searches of the CEA Registry at Tufts University, the NHS Economic Evaluations Database, the Health Technology Assessment Database, the Research Papers in Economics Database and PubMed. These will include NHS/PSS and societal costs where possible. We will aim to identify published estimates of incremental discounted lifetime costs from NHS/PSS and societal perspectives associated with main diagnosis leading to PICU admission. Where these are not available directly we will compute annual incremental costs by age and model lifetime costs applying survival estimates and recommended discount rates.[23] Given the uncertainty in these estimates we will undertake extensive sensitivity analyses (see below).

All costs will be reported in 2015/2016 prices, inflated where necessary using published inflation indices.[24]

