#### 8.1.2 DATA LINKAGE

#### 8.1.2.1 Purpose of data linkage

While PICANet data contain detailed clinical information regarding the transport, patient case mix, resource use and short-term outcome of transported critically ill children, there is limited information in PICANet regarding the patient pathway immediately prior to transport (such as length of time spent at the referring hospital and wards where the patient was cared for, whether admitted to the adult ICU for stabilisation prior to transport, and interventions performed). Linking PICANet data to HES data (and similar data from NHS Wales) for the acute hospital admission prior to transport and to CMP data (if the patient is admitted to an adult ICU) will provide a clearer understanding of the level of care provided to the child before transport to PICU - these factors are likely to significantly confound the association between timeliness of access to paediatric intensive care and clinical outcome. Therefore, it is crucial that information regarding pre-transport care is available for this study, which we plan to obtain from PICANet data linkage to HES and CMP. Similarly, PICANet data are limited to the PICU stay, which means that longer term outcomes of the patient such as 30- and 90-day mortality as well as healthcare resource use following PICU discharge are not available from PICANet. Data linkage to HES/ONS is vital to ensure that data related to 30-day mortality (study primary outcome), as well as other longer term clinical outcomes (secondary outcomes), is available.

See Appendix B for an example patient pathway for a critically ill child requiring transport to PICU.

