#### 8.3.4 ANALYSIS

Using these methods we will produce a patient-level dataset of costs and outcomes in the short-, medium- and long-run for every patient. Analyses of the mortality data will be as described above. QALYs will be analysed using a similar approach using linear models. Cost data are likely to be skewed and so to analyse these data (at 30 days, one year and lifetime) we will use a generalised linear model with gamma family and log link,[29] but will consider using other functional forms, such as Normal, Gaussian, inverse Gaussian and negative binomial distributions, selecting the model that gives the best fit of the data in terms of residual plots and the Akaike Information Criterion. We will also follow current guidance on conduct of economic evaluations using observational data to assess the main assumptions for addressing selection bias in the statistical models implemented.[30] The regression analyses will estimate lives saved, differences in costs, and QALYs gained between different PICRT models. Cost-effectiveness will be measured using incremental net monetary benefits (NMBs) calculated at different values of the willingness to pay to avoid one death or gain one QALY.

There will be considerable uncertainty in our estimates, especially in the long-run analysis. We will investigate this extensively using deterministic and probabilistic sensitivity analysis. Parametric and non-parametric bootstrap methods will be employed to evaluate uncertainty around differences in the lives saved, QALYs gained, costs and NMB, and we will construct cost-effectiveness acceptability curves.

The main outcome of the health economic analyses will be estimates of the costs and benefits of different PICRT models in the short-, medium- and long-run using a variety of cost and outcome measures, including point estimates and uncertainty intervals. We will follow current guidance for methods of technology appraisal to present and report the results of the economic analysis.[31] We will also estimate the budget impact if each PICRT model were to be rolled out nationally based on projections of need for PICRT services.

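### NHS care at the referring hospital between referral acceptance and departure is not costed, which favours any PICRT model with longer waits

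*Protocol*

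**What the plan says.** Protocol section 8.3.2 sets the scope: "There are three elements of the cost analysis: costs of PICRT transport; NHS/PSS costs in the" short and medium run, and NHS/PSS and societal costs in the long run. The content of each element is then given.

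- **Transport.** The cost is "based on travel time, team composition, interventions performed and management of critical incidents". These are the retrieval team's inputs.
- **Short and medium run.** The section says that "the main health care resource use categories following arrival at the PICU will include time spent in the PICU". It goes on to "time spent on different wards in the hospital after discharge from the PICU" and to admissions, A&E visits and outpatient visits up to one year.
- **Long run.** Lifetime costs by main diagnosis, taken from published sources.

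Section 8.3.1 fixes the viewpoint: "A UK NHS and personal social services (PSS) perspective will be adopted for the short- and medium-run analyses". It also dates the short-run outcome from the PICU: "We will evaluate costs and mortality at 30 days following PICU admission". Section 8.3.4 states the comparison: "The regression analyses will estimate lives saved, differences in costs, and QALYs gained between different PICRT models".

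On care before transport, section 8.1.2.1 plans linkage to HES, the Welsh equivalent and CMP, which "will provide a clearer understanding of the level of care provided to the child before transport to PICU". The use stated there and in section 8.1.3.4 is control of confounding in workstream A.

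**The concern.** A child waiting for a retrieval team is being looked after by an NHS hospital. Under an NHS perspective that care has a cost, and none of the three elements contains it. If every model had the same wait, the omission would cancel in an incremental analysis. Section 4.1.2 reports that waits differ widely between services, so it need not cancel.

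Two asymmetries follow from the text. An intervention is costed if the transport team performs it, but not if the general hospital team performs the same one before the team arrives, although section 8.1.3.4 says that the latter are recorded in PICANet. And PICU time is costed while waiting time is not, so any care moved from the PICU to the referring hospital passes from a costed to an uncosted setting.

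The incremental costs and net monetary benefits of section 8.3.4, and the budget impact estimated there, are built on this cost total. Section 8.4.1 would then combine the cost-effectiveness analysis with models that add teams or services to shorten time to bedside. The extra teams would be charged, while the referring-hospital time that they save would earn no credit.

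**Working it through.** The protocol gives no figure for this cost, so there is nothing to reproduce. The check has two parts: where the interval falls in the costing, and what the omission does to the comparison.

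**1. Locating the interval from acceptance to departure**

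| Cost element (8.3.2) | Covers referring-hospital care in the interval? |
|---|---|
| Transport | No. Only the retrieval team's travel, staffing, interventions and incident management |
| Short and medium run | No. Items begin at PICU arrival, and ward time begins at PICU discharge |
| Long run | No. Published lifetime costs by diagnosis |

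Hospital length of stay in section 8.1.3.1 does run from hospital admission, but it is a workstream A outcome and is not named as a cost item.

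**2. Direction**

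Let model S have the longer mean uncosted interval *h*_S, model F the shorter *h*_F, with hourly costs of waiting care *c*_S and *c*_F.

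- True cost difference (S − F) = planned cost difference + (*c*_S·*h*_S − *c*_F·*h*_F).
- With *c*_S = *c*_F = *c*, the missing term is *c*·(*h*_S − *h*_F), which is positive.
- Incremental net monetary benefit = willingness to pay × effect difference − cost difference. It is overstated for S by the same amount, whatever the willingness to pay.

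The direction depends on similar hourly costs. With intervals of 4 and 1 hours, it would reverse only if *c*_S were below one quarter of *c*_F.

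**3. Scale (illustration)**

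Inputs from section 4.1.2: median time to bedside from 1 to 4 hours, hence a 3-hour spread, and waits of up to 12 to 24 hours for some children in the winter surge. Assumed, not in the documents: referring-hospital care at GBP 500, 1,000 or 2,000 per day.

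Uncosted amount per child = daily cost × hours / 24.

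| Assumed cost per day | 3 hours | 12 hours | 24 hours |
|---|---|---|---|
| GBP 500 | 500 × 3/24 = about 62 | 250 | 500 |
| GBP 1,000 | 1,000 × 3/24 = 125 | 500 | 1,000 |
| GBP 2,000 | 2,000 × 3/24 = 250 | 1,000 | 2,000 |

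Time to bedside stands in here for acceptance to departure. Departure also depends on how long the team stabilises the child on site, and the protocol gives no acceptance-to-departure times.

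**The case against.** The strongest reply is that the list is open. It names main categories and says what they will include, and section 8.3.1 builds the costing dataset from the workstream A sources, which contain pre-transport HES and CMP data. An analysis plan could add the missing item. This shows that the data will be to hand. It does not move the starting point, which 8.3.2 sets at PICU arrival and 8.3.1 at PICU admission, and no other section adds hospital costs before that point.

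A second reply is that travel time is costed, so slower services already pay for delay. That is true for the retrieval team's journey. It does not cover the wait for a team to become free, or the referring hospital's own care during any wait.

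A third is that the sum may be small beside PICU stay, organ support and a year of hospital use. That may be so for typical waits. Section 8.3.2 makes a similar argument for primary care costs, yet estimates them and promises a sensitivity analysis. This interval gets neither.

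Some stronger readings do not stand. A reader might multiply the 3-hour difference by nearly 5,000 transports a year. Section 8.1.3.5 says that 85% of children are reached within 3 hours, so only about 15% (0.15 × 5,000 = 750) have a full 3 hours of wait that could be removed. The national product is therefore not a usable figure. A reader might also infer that the omission is as large as the cost contrast between models, or that it would reverse a recommendation. The documents give neither a transport cost nor a between-model cost difference. Nor do they say which models are slower: the 1 to 4 hours is a spread of medians, not a contrast between the models to be compared.

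**Conclusion.** The point holds. Followed as written, the plan assigns no cost to referring-hospital care between acceptance and departure, which is inconsistent with its NHS/PSS perspective. Every model's cost is understated. A model with longer waits is understated by more if the hourly cost of waiting care is similar, and incremental cost and net monetary benefit then lean towards it.

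The direction follows from the text under that one condition. The size does not: about GBP 62 to 250 per child for a 3-hour difference rests on the assumed daily costs and on time to bedside as a proxy. The GBP 500 to 2,000 for a 24-hour wait applies only to the few children who wait that long. The effect on the ranking of models cannot be judged from the documents. The case for change is that the gap is avoidable and lies in an interval that the study itself sets out to examine.

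**What to change.** In section 8.3.2, start short- and medium-run NHS costing at acceptance of the referral, keeping the 30-day and one-year end points where they are. Add a category for referring-hospital care from acceptance to departure, built from:

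- the transport times already in the study data (section 8.1.3.2 uses acceptance to bedside and acceptance to PICU arrival, and 8.3.2 already needs travel time);
- place of care from the linked HES/PEDW and CMP records;
- interventions by the general hospital team, as recorded in PICANet;
- NHS Reference Costs.

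Report net monetary benefit with and without this category, so that readers can see whether it matters.

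The change costs one added category and needs no new data source. Hourly costs must be apportioned from daily unit costs, and a place of care that the linked records do not separate will need an assumed unit cost. Both can be varied in the sensitivity analyses already planned in section 8.3.4.

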## 8.3.3 MEASURING OUTCOMES

For the short- and medium-run analysis, mortality up to one year will be measured directly in the study, as described in work stream A. Quality of life will be assessed at 12 months and used to compute QALYs for the medium-run analysis. As described previously, families will be consented during PICU admission for completion of quality of life questionnaires at 12 months follow-up. We expect most children to be under 5 years of age at PICU admission (approximately 50% of the transported children will be under 1 year of age, 25% will be aged 1-5 years, and 25% over 5 years). Measuring health-related quality of life suitable for estimating QALYs in this age group is

challenging, and we therefore propose to use two methods: HUI-2 measured via proxy assessment by the parent and the PedsQL mapped to EQ-5D scores.[25, 26] As children recruited to the study are initially critically ill, completion of quality of life measures at baseline will not be possible, and so as is normal in critical care studies an assumption about baseline quality of life for the cohort will be made, e.g. assume a value of zero at baseline.[27, 28] For survivors at 12 months, QALYs will be calculated using the utility scores at 12 months assuming utility score of zero at baseline, and a linear interpolation between baseline and 12 months. For decedents between baseline and 12 months, we will assume zero QALYs. For the long-run analysis, utility data will be obtained from published sources including: the CEA Registry at Tufts University, which contains a searchable database for utility weights by e.g. diagnosis; the NHS Economic Evaluations Database; and systematic searches of the wider literature for quality of life information suitable for estimating QALYs e.g. using PubMed.

#### 8.3.4 ANALYSIS

Using these methods we will produce a patient-level dataset of costs and outcomes in the short-, medium- and long-run for every patient. Analyses of the mortality data will be as described above. QALYs will be analysed using a similar approach using linear models. Cost data are likely to be skewed and so to analyse these data (at 30 days, one year and lifetime) we will use a generalised linear model with gamma family and log link,[29] but will consider using other functional forms, such as Normal, Gaussian, inverse Gaussian and negative binomial distributions, selecting the model that gives the best fit of the data in terms of residual plots and the Akaike Information Criterion. We will also follow current guidance on conduct of economic evaluations using observational data to assess the main assumptions for addressing selection bias in the statistical models implemented.[30] The regression analyses will estimate lives saved, differences in costs, and QALYs gained between different PICRT models. Cost-effectiveness will be measured using incremental net monetary benefits (NMBs) calculated at different values of the willingness to pay to avoid one death or gain one QALY.

There will be considerable uncertainty in our estimates, especially in the long-run analysis. We will investigate this extensively using deterministic and probabilistic sensitivity analysis. Parametric and non-parametric bootstrap methods will be employed to evaluate uncertainty around differences in the lives saved, QALYs gained, costs and NMB, and we will construct cost-effectiveness acceptability curves.

The main outcome of the health economic analyses will be estimates of the costs and benefits of different PICRT models in the short-, medium- and long-run using a variety of cost and outcome measures, including point estimates and uncertainty intervals. We will follow current guidance for methods of technology appraisal to present and report the results of the economic analysis.[31] We will also estimate the budget impact if each PICRT model were to be rolled out nationally based on projections of need for PICRT services.

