Sample Size	Quantitative analysis: PICANet data analysis on 15,000 transports performed			
	by PIC retrieval teams.			
	Questionnaires: 800-1000 completed transport questionnaires.			
	Interviews: 50 parents of critically ill children transported to PICU; 20-30			
	critically ill children transported to PICU; 35-40 clinicians involved in the care			

of critically ill children; 4-8 service managers/NHS commissioners.
Children and young people (age <16 years) transported by a PIC retrieval
team for emergency admission to a paediatric intensive care unit in England
and Wales.
None
Only the qualitative study will involve prospective patient recruitment. For
this part of the study, all emergency admissions to participating PICUs over a
12-month period will be screened for eligibility. Eligible patients will be
identified and consent sought for participation in the study.
Consent will be sought from parents/legal guardians for completion of
transport questionnaires; for potential contact with the researchers for
participation in an interview at a later date; and for future contact by a
researcher to administer quality of life questionnaires at 12 months.
Over a 12-month period, using questionnaires, we will gather feedback from
parents regarding the transport of their children.
We will conduct semi-structured interviews of parents to elicit their
experiences and perceptions regarding emergency transport to PICU (where
possible, the experiences of children themselves), 35-40 clinicians working in
acute general hospitals/PICUs/PICRTs, and service managers/commissioners.
We will collect follow up data at 12 months from parents/families regarding
the child's quality of life using validated questionnaires.

Table of Contents
-------------------

1		AMENDMENT HISTORY					
2	ABBREVIATIONS						
3	STUDY SYNOPSIS						
4	INTRO	DUCTION	13				
	4.1 Васк	GROUND					
	4.1.1	Centralisation of paediatric intensive care					
	4.1.2	Variations in access to paediatric intensive care and care delivered by PICRTs					
	4.2 STUD	Y RATIONALE					
	4.2.1	Clinical outcomes for transported critically ill children					
	4.2.2	Experiences of transported critically ill children and their families					
	4.2.3	Relevance to NHS service delivery					
	4.2.4	Timeliness of proposed research					
5	AIMS A	ND OBJECTIVES	16				
	5.1 STUD	Y AIMS					
	5.2 STUD	Y OBJECTIVES					
6	PROPO	SED RESEARCH OUTPUTS					
7		DESIGN					
8		CH PLAN					
Ū							

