# 7 STUDY DESIGN

DEPICT is a multi-disciplinary mixed-methods study comprising four linked work streams culminating in a series of workshops (See Appendix A for Study Flow Diagram):

A. Quantitative analysis of national paediatric intensive care audit data (PICANet) linked to routine administrative data (Hospital Episode Statistics in England and Patient Episode Database for Wales), death registrations (Office of National Statistics) and adult critical care data (Case Mix Programme).

[This analysis will be conducted retrospectively using data collected as part of national audit during a 3-year period between 2014 and 2016].

- B. Qualitative and questionnaire study involving interviews of parents of critically ill children transported to PICU (and children themselves, where feasible); interviews with clinicians working in PICUs, PICRTs and acute general hospitals and service managers/commissioners; and questionnaires to collect feedback from parents of transported children.
   [This workstream will involve prospective recruitment of patients over a 12-month period in 2017-18].
- C. Health economic evaluation of the costs and value for money of different models of PICRTs to identify cost-effective models of service delivery.
   [This workstream will involve analysis of costs and children's outcomes collected as part of the previous workstreams].
- D. **Mathematical modelling**, including the use of location-allocation optimisation, to explore the potential clinical and cost impact of alternative models of service and geographical locations where PICRTs could be based.

[This workstream will involve modelling using the findings of the previous workstreams].

E. **Workshops** involving key stakeholders: children and young people, parents, clinicians, and service managers/commissioners.

The study will involve the participation of all 10 PICRTs and 24 PICUs in England and Wales (representing 21 individual NHS Trusts).

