## 8.1.2.2 Study data and generating the linked dataset

We will extract relevant PICANet data related to the transport and the PICU admission episode from all transported admissions to participating PICUs in England and Wales with an admission date during a 3-year study period (1 Jan 2014 to 31 Dec 2016). To ensure a high-quality dataset, we will apply a series of data cleaning rules including individual data range checks and inter-variable validation to the study data set to identify and clean common and obvious data quality errors prior to analysis.

We will apply for HRA CAG approval for this study. See Appendix C for data flows during the linkage process.

Data linkage will be undertaken by the NHS Digital Data Access Request Service (DARS) acting as a 'trusted third party'. PICANet have experience of successfully linking PICANet data to HES/ONS data through HSCIC in the past. The availability of NHS numbers in a very high proportion of PICANet (98%) and CMP records for children (97%) provides reassurance that most records can be successfully matched using a minimal number of patient identifiers. PICANet data, including identifiers, is currently held at the University of Leeds. University of Leeds will upload a list of patient identifiers (NHS numbers, date of birth, name and postcode) and a unique DEPICT study number to secure servers at NHS Digital for a cohort of children admitted to PICUs in England

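### One-year QALYs cannot be computed as written for surviving children: measured utilities and linked one-year costs come from two cohorts that do not overlap

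*Protocol*

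**What the plan says.** The economic evaluation is built on workstream A. Section 8.3.1 states: "The data sources described in the quantitative analysis (workstream A) will be supplemented with cost data". Section 7 describes workstream A as "conducted retrospectively using data collected as part of national audit during a 3-year period between 2014 and 2016". Section 8.3.3 takes deaths up to one year from the same source, and section 8.3.2 counts hospital admissions and attendances over that year.

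Utilities come from elsewhere. Section 8.3.3 bases one-year QALYs on HUI-2 and mapped PedsQL scores at 12 months and says that "families will be consented during PICU admission for completion of quality of life questionnaires at 12 months follow-up". Only workstream B recruits families. The synopsis says: "Only the qualitative study will involve prospective patient recruitment". Section 7 gives the dates: "This workstream will involve prospective recruitment of patients over a 12-month period in 2017-18".

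Section 8.3.4 then promises that "we will produce a patient-level dataset of costs and outcomes in the short-, medium- and long-run for every patient". It plans linear models for QALYs, differences in QALYs and costs between PICRT models, net monetary benefit, bootstrap uncertainty and acceptability curves.

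**The concern.** The one-year analysis needs a utility, a cost and a survival status for each child. The protocol draws the first from one set of admissions and the other two from another. It does not say how they are to be brought together.

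The one-year QALY comparison of PICRT models is at stake, together with the net benefits and acceptability curves that rest on it. Section 8.4.1 intends to combine cost-effectiveness results with the service modelling, so the question does not stop at workstream C. If utilities are transferred by a rule chosen later, the interval depends on whether the uncertainty of the transfer is carried through. A QALY difference that really reflects survival and case mix could then be read as a quality-of-life difference observed between services.

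**Working it through.** The protocol gives no figure to reproduce on this point. The check traces which cohort supplies which input.

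**1. Inputs to the one-year calculation (section 8.3.3)**
- Child who dies within the year: QALY = 0. No utility is needed.
- Survivor: baseline utility is set to 0 and joined by a straight line to the 12-month score U. QALY = (0 + U)/2 × 1 year = U/2. The child's own U is the only input.
- Net monetary benefit (section 8.3.4): willingness to pay × QALY difference − cost difference. Costs must therefore be available as well.

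**2. What each cohort holds**

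| Item | Workstream A | Workstream B |
|---|---|---|
| Admissions | 1 Jan 2014 to 31 Dec 2016 (8.1.2.2) | 12 months in 2017-18 (7) |
| Contact with families | None; retrospective, pseudonymised (7, 9) | Consent and questionnaires (8.2.1) |
| One-year hospital use and deaths | Yes, by HES, ONS and Welsh linkage (8.1.2) | No linkage described |
| PICANet data | Yes | By consent (8.2.1, 9) |
| 12-month utility | None | Yes, if returned |

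Section 8.1.2.1 itself says that PICANet does not hold later mortality or healthcare use after PICU discharge. PICANet extraction therefore cannot complete the workstream B column.

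**3. Overlap of index admissions**
The most generous reading of workstream B is 1 January 2017 to 31 December 2018. The overlap with workstream A is max(0, 31 Dec 2016 − 1 Jan 2017 + 1 day) = 0 days. A child admitted in both windows could belong to both cohorts, but the utility would be timed from a different admission.

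**4. Size of the gap**
- Transports in workstream A: about 15,000 (8.1.3.5).
- Deaths by 30 days at about 7% (8.1.3.5): 0.07 × 15,000 = 1,050, each with a cost and a QALY of zero.
- Remainder: 15,000 − 1,050 = 13,950. One-year mortality is not given, so the number of one-year survivors is somewhat lower.
- Workstream A survivors with a measured utility: 0.

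For scale only: the protocol gives no expected number of 12-month returns. Its one questionnaire total, 800 to 1000, is for the transport form. That equals 800/15,000 = 5.3% to 1000/15,000 = 6.7% of the workstream A count, and comes from different admissions.

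**5. Is there a bridge?**
Section 8.3.3 names published utilities for the long-run analysis only. Nothing in sections 8.3.1 to 8.3.4 assigns a workstream B utility to a workstream A child.

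**The case against.** The strongest defence is that a value for each patient need not be a measured value. Workstream C already assigns values: primary care costs from published estimates by diagnosis, lifetime costs and utilities from the literature, and a baseline utility of zero. Section 7 says that workstream C uses material from the earlier workstreams together, so combining A and B is plainly intended. On this view only a transfer method is missing, and an analysis plan may supply it.

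Part of this stands: the intention to combine is visible. But where section 8.3 assigns values it says so and names the source. For one-year QALYs it instead specifies a calculation from each survivor's 12-month score, and the stated data cannot feed that calculation. This goes beyond an omitted detail.

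A reader might infer more than the documents support:
- *That no patient at all has both a cost and a QALY.* Workstream A children who die within the year have both.
- *That the whole economic evaluation fails.* The 30-day analysis uses costs and deaths, and the long-run analysis uses published utilities. Section 8.3.1 already makes lives saved the primary health outcome, with QALYs secondary, so there is no need to ask for a change of headline measure.
- *That the number of utilities per retrieval team can be predicted.* The 20-25% in section 8.2.2 is a postal rate for the transport questionnaire. The 12-month measure is a separate consent item followed up by a researcher, and its return rate is not stated.
- *That average utilities will be substituted without saying so.* The protocol does not say this, and section 8.3.4 promises extensive sensitivity analysis.

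**Conclusion.** The point holds for one secondary outcome at one of three time horizons. No index admission of a child who survives to one year has both a measured 12-month utility and linked one-year hospital costs and death status. The section 8.3.3 calculation, and the section 8.3.4 promise for the medium run, cannot be carried out as written.

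The gap covers every one-year survivor in workstream A: at most about 13,950 of 15,000 transports, using the protocol's rounded count and 30-day mortality. The finding itself needs neither figure. It rests on the stated admission windows and on the absence of any HES or ONS linkage for workstream B families. If such linkage were added, costs and utilities could be paired for respondents in 2017-18, but the workstream A survivors would still have no measured utility.

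**What to change.** In sections 8.3.3 and 8.3.4, limit the patient-level promise to what the data give, and replace it for one-year QALYs with an explicit two-cohort method:

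1. Fit a utility model in the 12-month respondents on pre-PICU covariates available through PICANet in both cohorts, for example age, diagnosis, PIM-2 and comorbidity. Leave out PICU length of stay, which section 8.1.3.1 lists as a study outcome and which PICRT care may affect.
2. Predict utilities for workstream A one-year survivors by multiple imputation, and redraw the utility-model parameters within each bootstrap sample. Keep zero QALYs for deaths.
3. Address non-response among consented families where their PICANet data allow. State that refusal is not corrected, because the plan provides no 2017-18 PICANet data on families who do not consent.
4. Report one-year QALY differences between PICRT models as modelled, driven by survival and by the covariates in the utility model, and not as measured differences in quality of life.

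Before fixing the covariate list, reconcile the scope of consent: section 8.2.1 refers to PICANet data on the transport episode, while section 9 adds the PICU admission.

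The cost is rewording, some extra modelling and wider QALY intervals. No new data collection is needed.
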